Initial investigations from the largest ever adjuvant study conducted in patients with breast cancer, the ATAC trial involving over 9000 patients, were presented in San Antonio in 2001 [36]. The results showed that anastrozole is statistically significantly more effective in reducing early relapses than tamoxifen ($p=0.013$). However, it should be noted that at this point in time, the mean duration of therapy and the mean retention time of patients in the study were between 30 and 36 months and thus the duration of therapy of 5 years stated in the study was not reached by a long shot. Therefore, at this point in time tamoxifen is still to be considered the treatment of choice, although the hope is that anastrozole will also show a benefit over tamoxifen at the 5-year treatment duration point.

The adverse effect profile is shown in Table 2. This shows a significant reduction in the occurrence of endometrial cancer and vaginal bleeding as well as thromboembolic episodes, stroke and hot flushes in the anastrozole-treated group compared to the tamoxifen-treated group. However, musculoskeletal symptoms, especially joint pain, and fractures are significantly more common with anastrozole. Other significant side effects, such as fatigue, changes in emotional state, ischaemic cardiovascular disease and cataracts are not significantly different.

As interaction studies with antipyrine and cimetidine showed, it is unlikely that concomitant administration of Arimidex[®] with other medicines leads to clinically significant, cytochrome P450-mediated drug interactions. Furthermore, safety data from clinical studies showed no evidence of clinically significant interactions between Arimidex[®] and other commonly prescribed medications. Oestrogen-containing therapies should not be administered together with Arimidex[®], since they could neutralise its pharmacological effect.

A dose of anastrozole of up to 10 mg does not cause any change in the secretion of cortisol or aldosterone. Interactions with bisphosphonates are yet to be established.

Table 2: Adverse effects ATAC trial in % [36]

	Anastrozole (n = 3125)	Tamoxifen (n = 3116)	Combination (n = 3125)
Hot flushes	34.3	39.7	40.2
Nausea & vomiting	10.5	10.2	11.7
Fatigue (asthenia)	15.7	15.1	14.0
Mood swings	15.5	15.2	15.6
Muscle and joint problems	27.8	21.2	22.1
Vaginal bleeding	4.5	8.1	7.7
Vaginal discharge	2.8	11.4	11.4
Endometrial cancer*	0.1	0.5	0.2
Fractures overall	5.8	3.7	4.6

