9.1 Definition of “adverse event – (AE)”

An adverse event is the occurrence of a disorder or exacerbation of a pre-existing condition in the context of a clinical study and is independent of a possible causal relationship with the administration of the trial drug. Disorders may be subjective and objective symptoms of the disease, including laboratory abnormalities. Adverse events leading to discontinuation of therapy must be documented in both the medical history and in the CRF.

With the exception of AEs that lead to discontinuation of therapy and fractures, all other AEs that are non-serious are not documented in the CRF within this study. However, it is mandatory to record all adverse effects in the patient’s medical file.

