10.5. Safety analysis

The safety analysis is based on all randomised patients who started the therapy. All serious adverse events, adverse events leading to therapy discontinuation and fracture rates observed during or after therapeutic administration of the study drug are recorded. The worst value per patient is included in the analysis.

[figure not shown]
The laboratory data measured is described and maximum and minimum measurements are presented over time or by maximum deviations from the normal range. In addition, absolute and percentage changes from the baseline measurement values and maximum fluctuations over time are described.

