### 3.4.1. Disposition of patients

Recruitment, discontinuation from study including reasons for discontinuation, as well as patient disposition and discontinuation from treatment including reasons for discontinuation will be summarized overall and by treatment arm.

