## 3.7. Safety evaluation

Analyses of the safety data are based on the SAF population. Only serious adverse events (SAEs) and adverse events (AEs) leading to discontinuation of the therapy are collected in this trial. Frequencies of serious adverse events will be summarized descriptively per treatment arm and in total. Patient listings of SAEs and of AEs leading to discontinuation of the therapy will be given. Change in tumor markers CEA and CA 15-3 will be descriptively summarized (e.g., means, median, standard deviations, ranges).

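### SAP 3.7 only lists AEs that end therapy, so no by-arm summary by event type or period is planned for the one CRF route open to non-serious joint pain

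*SAP*

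**What the plan says.** **Collection.** Protocol 9.1 limits what is entered: apart from "AEs that lead to discontinuation of therapy and fractures, all other AEs that are non-serious are not documented in the CRF". SAP 3.7 describes the scope more narrowly: "Only serious adverse events (SAEs) and adverse events (AEs) leading to discontinuation of the therapy are collected in this trial". Fractures nevertheless have their own survey at visits and are a secondary endpoint (SAP 3.6.4). Amendment 1 adds a query on new hepatic or renal insufficiency at the 12- to 60-month visits.

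**Protocol analysis.** Section 10.5 covers every randomised woman who began taking the drug, and states: "All serious adverse events, adverse events leading to therapy discontinuation and fracture rates observed during or after therapeutic administration of the study drug are recorded". It adds that each patient contributes her worst value.

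**SAP analysis.** Section 3.7 treats the two kinds of event differently. For serious events: "Frequencies of serious adverse events will be summarized descriptively per treatment arm and in total". For AEs that end therapy: "Patient listings of SAEs and of AEs leading to discontinuation of the therapy will be given".

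**Elsewhere in the SAP.** Section 3.4.1, on the ITT population, states that "discontinuation from treatment including reasons for discontinuation will be summarized overall and by treatment arm". The reason categories are not given, and neither event type nor a time base is mentioned. Section 4, on departures from the protocol, does not discuss the handling of these AEs.

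**The concern.** The trial asks whether three more years of anastrozole are worth having, so the harm of those years is half of the answer. Protocol 2.3.2 names the harms to expect: "musculoskeletal symptoms, especially joint pain, and fractures are significantly more common with anastrozole". In its Table 2, muscle and joint problems occur in 27.8% on anastrozole and 21.2% on tamoxifen. The difference of 6.6 points is the largest excess for anastrozole in that table; for all fractures it is 5.8% against 3.7%, or 2.1 points.

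The SAP treats these two harms very differently. Fractures get a log-rank comparison from year 2. Joint pain that is not serious enters the CRF only when it ends therapy, and those events go into a listing. The report could then appear without a musculoskeletal figure for either arm. The nearest by-arm number, the count of reasons for stopping, would be hard to read because the arms are on drug for different lengths of time.

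**Working it through.** The documents give no rate of stopping for an AE, so there is no plan figure to reproduce. The check has two parts.

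**1. What is planned for each recorded harm**

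| Harm | How it reaches the CRF | Planned by-arm output |
|---|---|---|
| Serious AEs | SAE reporting (protocol 9.3) | Frequencies by arm (SAP 3.7) |
| Fractures | Fracture survey (protocol 7.2, 9.1) | Log-rank test from year 2 (SAP 3.6, 3.6.4) |
| Hepatic or renal insufficiency | Query at visits (Amendment 1) | None specified in SAP 3.7 |
| Non-serious joint pain | Only if it ends therapy (protocol 9.1) | Listing (SAP 3.7), plus whatever the reasons for stopping in SAP 3.4.1 show |

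The adherence analysis in SAP 4.2.3.1 does not fill the gap. It classes early stops for any reason other than recurrence or death as non-adherent, so AE stops are pooled with the rest.

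**2. What a crude by-arm count would show**

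Inputs:
- Time on drug: 2 years in Arm A, 5 years in Arm B (both documents).
- Women per arm: 3,500 / 2 = 1,750, assuming 1:1 allocation.
- Yearly hazard h of stopping for an AE: assumed constant and equal in both arms, range 0.02 to 0.05, with no competing loss.

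Formulas:
- Crude proportion, Arm A: 1 − exp(−2h)
- Crude proportion, Arm B: 1 − exp(−5h)
- Arm B stops after month 24: 1,750 × [exp(−2h) − exp(−5h)]

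| h per year | Arm A | Arm B | Ratio B/A | Arm B stops after month 24 |
|---|---|---|---|---|
| 0.02 | 3.9% | 9.5% | 2.43 | 98 |
| 0.03 | 5.8% | 13.9% | 2.39 | 142 |
| 0.05 | 9.5% | 22.1% | 2.32 | 221 |

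Every row has the same yearly rate in both arms. Per 100 patient-years on therapy, each arm would show 100h, that is 2, 3 or 5. The whole ratio comes from exposure.

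**Sensitivity to competing loss.** SAP 2.4 considers a 7% exponential drop-out. Taking this as 7% a year (an assumption) and applying it to both arms, the proportion stopping for an AE by time t is [h/(h + 0.07)] × [1 − exp(−(h + 0.07)t)].
- h = 0.02: Arm A 3.7%, Arm B 8.1%, ratio 2.20; Arm B stops after month 24 about 77.
- h = 0.05: Arm A 8.9%, Arm B 18.8%, ratio 2.11; Arm B stops after month 24 about 173.

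The counts fall by about a fifth, and the ratio stays above 2.

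**The case against.** A reader might infer that the tolerability of the extra years is never compared between arms. The documents do not support that. Serious AEs are tabulated by arm, fractures are tested from year 2, and SAP 3.4.1 gives reasons for stopping by arm. Nor are AE stops the only CRF entry for non-serious harm in general: fractures and hepatic or renal insufficiency are recorded separately. The statement holds for non-serious joint pain.

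It is also tempting to say that the SAP breaks a protocol commitment without declaring it. Protocol 10.5 says that these events are recorded and that the worst value per patient is analysed. It does not promise frequencies by type and arm. The SAP delivers less than 10.5 suggests, but no explicit undertaking is broken.

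Further points against:
- Table 2 compares anastrozole with tamoxifen, not continuing with stopping anastrozole. It shows which harm to look for, not its size here.
- The reason categories in SAP 3.4.1 are not listed. The section may yield an AE row or something finer; the documents do not say.
- The cumulative proportion stopping for an AE under a 5-year against a 2-year assignment is a legitimate quantity, because longer exposure is what was randomised. It does not measure yearly toxicity, so a rate should stand beside it.
- After month 24 Arm A is off drug and cannot stop for an AE. No SAP wording can turn that period into a like-for-like comparison; the limit comes from what protocol 9.1 collects.

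All of this stands, and it narrows the point. What remains is that the events most informative about non-serious joint pain have no planned summary by type, arm or period.

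**Conclusion.** The point holds as a reporting gap that is cheap to close. SAP 3.7 reduces AEs that end therapy to listings, and the remaining by-arm information is the reasons for stopping, on the ITT set with no stated event type or time base, together with the fracture endpoint. If the only by-arm figure were a crude count of AE stops, equal yearly rates would produce a 2.3- to 2.4-fold difference, or about 2.1- to 2.2-fold with 7% yearly loss to other causes. Between about 77 and 221 Arm B women would stop for an AE in the extra treatment period under the same range of assumptions.

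These sizes rest on an assumed constant hazard of 2-5% a year and 1,750 women per arm; the documents supply no AE-stopping rate. The exposure argument depends little on the hazard chosen, but the counts depend on it directly. No efficacy endpoint or error rate is affected.

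**What to change.** In SAP 3.7, keep the listings and add a descriptive table of AEs leading to discontinuation on the SAF population:
- by arm and by event type, with a musculoskeletal/joint row;
- as number and percentage of women, and as rate per 100 patient-years on therapy;
- for months 0-24 in both arms, and for months 24-60 in Arm B.

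State in the text that months 24-60 show Arm B incidence during the extra treatment and are not a between-arm test. Note the addition against protocol 10.5.

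The events are already in the eCRF, and SAP 4.2.3.1 already derives treatment duration from documented start and end of therapy, so the denominators need no new data. The cost is coding the AE terms for this subset and one or two extra tables. The documents do not describe the AE term field, so check first that its entries can be coded.

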## 3.8. Exploratory analyses

Exploratory analyses will be based on the ITT population.

### 3.8.1. Subgroup analyses

DFS will be analyzed using Cox proportional hazard models within each of following subgroups:

- Age group: age  $\leq$  60, age  $>$  60
- Tumor stage: T1, T2 and T3
- Histological grade: Grade I, Grade II, Grade IIIs
- Hormone receptor status: ER+/PgR+, any negative
- Previous hormone therapy: Tamoxifen, Tamoxifen+AI, AI
- Previous chemotherapy: any chemotherapy, no chemotherapy

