10.4. Efficacy analysis

The final analysis is carried out according to the intent-to-treat principle of all randomised patients who meet the inclusion and exclusion criteria, have at least one follow-up examination after randomisation, and have survived for 2 years relapse free. They will be assigned to the group into which they were randomised regardless of whether they actually received the therapy or which one.

The graphical representation of the therapeutic effect on the primary and secondary target variables (DFS, overall survival and occurrence of secondary cancers, contralateral breast cancer and fractures) is based on the survival functions according to Kaplan and Meier (1958). The differences between the two study arms are tested using the log-rank test (Mantel (1966)).

In addition, the regression model according to Cox (1972) is used in an exploratory way to examine whether the consideration of additional prognostic factors modifies the results of the log-rank tests. This takes into account primarily the stratification criteria of the randomisation but also other prognostic factors. Differences in the therapy are quantified using hazard ratios (relative mortality risk during therapy compared with the control group). In addition, possible interactions of the therapy with other prognostic factors are examined. In the event of significant interactions, subgroup analyses are carried out.

All calculations are performed using the statistical software SAS® (Statistical Analysis Software; version 8) and all tests are two-tailed, where $p \leq 0.05$ is deemed statistically significant.

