11.3. Data management (data review)

The eForms marked as source data verified by Monitoring are checked for consistency and plausibility by Data Management. Any queries (=discrepancies) are generated via the Internet and are therefore visible to both the investigator and monitor as soon as they are created in the system by means of "marks" (icons). Data Management locks all eForms that it finds to be fully correct, meaning they are protected from further processing. "Marks" indicate this processing status.

The individual working steps carried out by Data Management are specified in SOPs (= standard operating procedures) and WIs (= working instructions).

Justification for the amendment:

- The age limit in the inclusion and exclusion criteria is being raised (reason: there are a number of sprightly patients who will tolerate the study follow-up phase well and can remain compliant. The primary objective of the study will not be affected by a potential increase in the incidence of deaths that are not breast cancer related.)
- Correction of the permitted N-stages of the tumour from N1 to N+ (reason: it is expected that all patients, regardless of their N-stage at the time of diagnosis will benefit from extending the therapy with anastrozole beyond 5 years)
- Addition to the exclusion criterion: "Manifest secondary malignancy or status post secondary malignancy" with the following exceptions: a) simultaneous bilateral breast cancer, oestrogen and/or progesterone receptor-positive on both sides at the time of diagnosis (reason: because of the simultaneity of the tumour occurrence, such a carcinoma is interpreted as a multi-centric carcinoma); b) in-situ carcinoma of the cervix and basal cell carcinoma of the skin, is a correction of the data in the CRF and protocol, as these exceptions were defined in the CRF (reason: the probability of relapse in these carcinomas is minimal.)
- Extension of the recruitment phase for 1 year (reason: the annual recruitment rate was overestimated in the study planning phase.)

- The flow chart will be adjusted following the protocol amendments as per Amendment 1.
- The Data Management System of ABCSG is being changed from the PDF-format based IntTrial® system (CRS – Creative Research Solutions GmbH) to the web-based MACRO® data management system (software from InferMED). This change was prompted by the withdrawal of support for IntTrial® on the part of the system developer.

Initiators of the amendment:

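### SAP 3.8.1 fits separate Cox models in 14 or 15 subgroups with no interaction test and no nodal-stage subgroup, an unrecorded departure from protocol 10.4

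*SAP*

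**What the plan says.** Protocol 10.4 sets an order for the exploratory Cox work. It considers mainly the stratification criteria, examines possible interactions of therapy with prognostic factors, and then: "In the event of significant interactions, subgroup analyses are carried out". It also sets p≤0.05, two-sided, as the threshold for all tests.

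SAP 3.8.1 starts at the last step: "DFS will be analyzed using Cox proportional hazard models within each of following subgroups". The six factors and their levels are:

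- age, split at 60 years (two levels)
- tumour size category, written as "Tumor stage: T1, T2 and T3", which can be read as three levels or as two
- grade (three levels)
- receptors, both positive or not (two levels)
- type of earlier endocrine treatment (three levels)
- chemotherapy before entry, yes or no (two levels)

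The section contains no arm-by-factor term and no condition for running the models. It gives no rule for reading the results. It sits under 3.8, exploratory analyses in the ITT population.

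Three other places matter:

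- SAP 4.2.3.2 specifies a Cox model for DFS with therapy group, type of previous endocrine therapy and their interaction, for the advanced analysis.
- SAP 3.8.2 includes pN stage as a covariate in the multivariable models.
- SAP section 4 lists changes from the protocol (interim analysis, analysis population, start time, added exploratory objectives). The change in subgroup method is not among them.

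**The concern.** Whether five further years rather than two helps some patients more than others is a question about interaction. Separate models in each level do not answer it. A level with p below 0.05 beside one with p above 0.05 is not evidence that the two effects differ. Two misreadings become easier: a chance result reported as benefit in one group, and a real effect judged absent in a small group.

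Because section 4 is silent, a reader would assume that the protocol's interaction-first rule still applies.

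Nodal stage raises a separate question of coverage. pN is a stratification factor, and Amendment 2 widened nodal eligibility on the ground that "it is expected that all patients, regardless of their N-stage at the time of diagnosis will benefit". Adjusting for pN as a covariate deals with its prognostic effect. It does not show whether the treatment effect varies with it.

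**Working it through.** **1. The plan's own design figure.** Protocol 10.1 and SAP 2.4 state 433 events for 85% power at a hazard ratio of 1.35, two-sided 5%. The Schoenfeld formula with 1:1 allocation (assumed, as no ratio is stated) gives 4(1.960 + 1.036)²/(ln 1.35)² = 399 events. Freedman's gives 405. With 433 events the power is 87–88%. The stated figure therefore does not reproduce exactly, but nothing below depends on that. I use 433 as the planned number.

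**2. Number of subgroup models.** The levels are age 2, tumour stage 3, grade 3, receptor status 2, previous hormone therapy 3 and chemotherapy 2. The total is 15, or 14 if T2 and T3 are read as one group.

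**3. Chance of at least one nominal p≤0.05 when the arms do not differ.** The documents state no such rate. If the tests were independent:

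- 15 tests: 1 − 0.95¹⁵ = 53.7%
- 14 tests: 1 − 0.95¹⁴ = 51.2%
- six interaction tests: 1 − 0.95⁶ = 26.5%
- seven interaction tests, with pN: 1 − 0.95⁷ = 30.2%

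The subgroup tests are not independent, because all six factors divide the same events. I therefore simulated 4,000 null trials per setting. Each event fell in either arm with probability one half, and factor levels were drawn independently of each other. Each level was tested by z = (b − n/2)/√(n/4), where b of its n events fall in one arm. Interactions were tested by heterogeneity across levels.

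The documents give no subgroup shares, so these are assumed. The unequal set is age 40/60, T 70/25/5, grade 20/60/20, receptor 75/25, hormone therapy 50/43/7 and chemotherapy 30/70. The total of 750 events is also assumed.

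| Shares | Levels | Events | Any subgroup p≤0.05 | Any interaction p≤0.05 |
|---|---|---|---|---|
| Unequal | 15 | 433 | 41.7% | 27.0% |
| Unequal | 15 | 750 | 40.5% | 26.0% |
| Equal | 15 | 433 | 40.8% | 27.7% |
| Equal | 15 | 750 | 39.8% | 26.8% |
| Unequal, T 70/30 | 14 | 433 | 38.3% | 27.3% |
| Unequal, T 70/30 | 14 | 750 | 37.5% | 26.0% |

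**4. Power within one subgroup at a hazard ratio of 1.35.** With d events, power = Φ(√d · ln(1.35)/2 − 1.960).

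| Share of events (assumed) | Of 433 events | Of 600 events (assumed) |
|---|---|---|
| 20% | d = 86.6: 29% | d = 120: 38% |
| 30% | d = 129.9: 40% | d = 180: 52% |

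The second column is there because SAP 3.2 says the required number of events had long been reached, so the analysis will probably have more than 433.

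**The case against.** The strongest reply is that nothing confirmatory depends on 3.8.1. The analyses are labelled exploratory, the section sets no threshold or decision rule, and a fixed list of six factors is tighter than the protocol's open reference to other prognostic factors. That stands, and it limits the weight of the point. It does not explain why a method that cannot test effect modification replaced one that can, or why the change went unrecorded.

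A reader might draw stronger conclusions that the documents do not support:

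- *That the SAP has no interaction test at all.* Section 4.2.3.2 has one, for one of the six factors, in the advanced analysis. The gap is in 3.8.1.
- *That false subgroup findings are likely.* About 40% is below one half. The fair comparator is about 26% for six interaction tests, so the excess is roughly 10 to 15 points. The rate exceeds one half only if overlapping subgroups are treated as independent.
- *That nodal stage is ignored, or that its omission breeds chance findings.* It is a covariate in 3.8.2. Leaving a factor out reduces the number of tests, and adding it raises the figure for interaction tests from 26% to 30%.
- *That Amendment 2 set up a nodal subgroup hypothesis.* Its sentence justifies eligibility, calls the change a correction, and if anything expects a uniform effect. The original strata already included 4–9 and 10 or more nodes.

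Interaction tests also have low power. For two equal halves of 433 events, the standard error of the difference in log hazard ratios is √(4/216.5 + 4/216.5) = 0.192. For the overall effect it is √(4/433) = 0.096. A non-significant interaction is therefore not proof of a uniform effect.

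**Conclusion.** The point holds as a cheap improvement to an exploratory section. SAP 3.8.1 departs from protocol 10.4, section 4 does not say so, and the method chosen cannot answer the subgroup question. The lack of a pN subgroup is a separate gap: as written, the plan cannot examine whether the effect differs by nodal stage.

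The false-finding rates of 38–42% and about 26% rest on assumed subgroup shares, independently distributed factors and a nominal 5% threshold taken from the protocol, since 3.8.1 states none. They also describe different claims: an effect within a level, and a difference between levels. The 29–40% power range rests on the planned 433 events and shares of 20–30%. With an assumed 600 events it becomes 38–52%. The primary DFS result is unaffected.

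**What to change.** In SAP 3.8.1:

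- For each factor, fit one Cox model for DFS with arm, factor and arm-by-factor, and report the interaction p-value.
- Present subgroup hazard ratios with confidence intervals as estimates only, without subgroup p-values.
- Add pN stage as 0, 1–3, and 4 or more nodes, which collapses the four strata already collected.
- State whether T2 and T3 form one level or two.

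In SAP section 4, record that subgroup estimates are shown whatever the interaction result, as a change from protocol 10.4. This entry is needed because the proposed analysis also departs from the protocol's condition.

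The cost is SAP wording, a few lines of code and one more factor to report. No new data are needed, and 4.2.3.2 already uses the same type of model.
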